
Thrombosis and tissue ischemia events will be considered to be secondary to excessive erythropoiesis if during the window of [AE start date – 30 days, AE start date +15 days] any one of the following 3 events occurs:
 
 • Any Hgb value \geq 13 g/dL (measured pre-dialysis) • Hgb increase $>$ 2 g/dL over 2 weeks (+1 week) 
 ○ Note: for programming purposes, a +1 week window is applied, corresponding to the allowable visit window, to look for increases $>$ 2 g/dL over 3 weeks • Hgb increase $>$ 4 g/dL over 4 weeks (+1 week) 
 ○ Note: for programming purposes, a +1 week window is applied, corresponding to the allowable visit window, to look for increases $>$ 4 g/dL over 5 weeks 
To identify Hgb increases that meet the increase criterion above, all Hgb values taken within [AE start date – 58 days, AE start date + 15 days] will be identified. This corresponds to identifying Hgb values that occurred 4 weeks before the [AE start date – 30 days, AE start date +15 days] window of interest. HemoCue Hgb and central laboratory Hgb values will then be evaluated separately to identify increases, so that HemoCue and central laboratory Hgb values are not compared to each other to identify an increase.
 
For HemoCue Hgb and separately for central laboratory Hgb values, if there is a Hgb value (or daily Hgb average) within the [AE start date – 30 days, AE start date +15 days] window and an earlier Hgb value (or daily Hgb average) that is within the larger [AE start date – 58 days, AE start date + 15 days] window, and the amount of time between the two Hgb values is:
 
 • Between 1 day and 3 weeks, inclusive, then the Hgb values will be compared to determine if there has been a Hgb increase $>$ 2g/dL. • Between 15 days and 5 weeks, inclusive, then the Hgb values will be compared to determine if there has been a Hgb increase $>$ 4g/dL. 
Unscheduled Hgb values will also be used in the assessment of secondary to excessive erythropoiesis following the guidance specified in Section 10.6.3 for unscheduled Hgb values and multiple Hgb values on the same date.

Pre-defined Lists of AE Preferred Terms Corresponding with Each AESI
 
Thrombosis and/or tissue ischemia secondary to excessive erythropoiesis
 
 • Narrow SMQ: Embolic and thrombotic events, arterial

CONFIDENTIAL

201410

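### The Hgb look-back for thrombosis or ischaemia secondary to excessive erythropoiesis is 58 days, 7 days short of the 65 that the SAP's own 5-week comparison requires (minor)

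*SAP*

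**What the plan says.** SAP Section 10.6.4.3 first picks out candidate thrombosis and ischaemia events from a list of terms. It then applies haemoglobin criteria to each. An event is "considered to be secondary to excessive erythropoiesis if during the window of [AE start date – 30 days, AE start date +15 days"] at least one of three things happens: an Hgb of 13 g/dL or more, a rise above 2 g/dL over 2 weeks, or a rise above 4 g/dL over 4 weeks.

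For both rise criteria the SAP adds a programming tolerance: "a +1 week window is applied, corresponding to the allowable visit window". The 2-week criterion is therefore programmed over 3 weeks and the 4-week criterion over 5 weeks. The comparison bullets carry this through. For the 2 g/dL rise: "Between 1 day and 3 weeks, inclusive, then the Hgb values will be compared". For the 4 g/dL rise: "Between 15 days and 5 weeks, inclusive, then the Hgb values will be compared".

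The retrieval step uses a different length. It reads "all Hgb values taken within [AE start date – 58 days, AE start date + 15 days] will be identified", and the SAP accounts for the 58 days as follows: "This corresponds to identifying Hgb values that occurred 4 weeks before the" window of interest. The limit appears a second time as a condition of the comparison itself, which needs a later value in the window of interest and "an earlier Hgb value (or daily Hgb average) that is within the larger [AE start date – 58 days, AE start date + 15 days] window".

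**The concern.** The extra week lengthens the interval over which two values may be compared, but not the period from which the earlier value may be drawn. A programmer who follows the text must discard some pairs that the next bullet says to compare.

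Intervals of 29 to 35 days are to be expected. After Week 8 the scheduled visits are 4 weeks apart, with a window of plus or minus 1 week from Week 6 onwards, and Protocol Section 7 lets visits be up to 5 weeks apart. Protocol Table 6 schedules no central laboratory haematology at Weeks 2 and 6, so scheduled central values are nominally 28 days apart throughout. The SAP assesses central and HemoCue values separately, so for scheduled central values the 4 g/dL criterion is the main rise rule.

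At stake is the count for one adverse event of special interest, which SAP Section 8.2.3.2 reports by arm as number, percentage and rate per 100 person-years. A retrieval window that is too short can remove qualifying events from that count but cannot add any.

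**Working it through.** **Inputs**, all from SAP Section 10.6.4.3, in days relative to the event start:

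- later value: day -30 to day +15, which is 46 possible days
- earliest retrieved value: day -58
- interval for the 4 g/dL rise: 15 to 35 days, which is 21 possible intervals
- interval for the 2 g/dL rise: 1 to 21 days, which is also 21 possible intervals

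**The plan's own figure.** Look-back = lower edge of the window of interest + comparison interval. With 4 weeks this gives 30 + 4 × 7 = 58, the stated figure.

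**Look-back that the stated rules need.**

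- 4 g/dL rise over 5 weeks: 30 + 5 × 7 = 65, a shortfall of 65 - 58 = 7 days
- 2 g/dL rise over 3 weeks: 30 + 3 × 7 = 51, inside 58, so nothing is lost

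**Which pairs are lost.** A pair is lost when later day - interval < -58.

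| Day of later value | Intervals lost (days) | Number |
|---|---|---|
| -30 | 29 to 35 | 7 |
| -29 | 30 to 35 | 6 |
| -28 | 31 to 35 | 5 |
| -27 | 32 to 35 | 4 |
| -26 | 33 to 35 | 3 |
| -25 | 34 to 35 | 2 |
| -24 | 35 | 1 |
| -23 to +15 | none | 0 |

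The total is 7 + 6 + 5 + 4 + 3 + 2 + 1 = 28. There are 46 × 21 = 966 permitted day/interval combinations, so 28/966 = 2.9% are cut off. Among intervals of 29 to 35 days alone the count is 28 of 46 × 7 = 322, or 8.7%. With a look-back of 65 days the number lost is 0 of 966.

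**An example with assumed values.** Hgb is 8.2 g/dL on day -62 and 12.5 g/dL on day -28. The rise is 12.5 - 8.2 = 4.3 g/dL over 62 - 28 = 34 days. It meets the 5-week rule and the later value is below 13 g/dL, but day -62 lies outside the 58-day window, so the pair is never compared.

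**When the loss changes a classification.** The 13 g/dL trigger needs no pair. For the loss to matter, every value in the window of interest must be below 13 g/dL. With a rise above 4 g/dL, the earlier value must then be below 13 - 4 = 9 g/dL. That is possible, since Protocol Section 5.1 admits patients with Hgb of 8 to 11.0 g/dL at randomization. No other pair, central or HemoCue, may meet either rise rule.

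**The case against.** The clinical criterion is a rise over 4 weeks, and the fifth week is only a programming tolerance. With 58 days, every pair up to 28 days apart whose later value is in the window is retrieved. On this view 58 may be a deliberate 4-week look-back. The first part stands: only pairs that qualify through the tolerance are lost. The second does not remove the contradiction. Both the programming note and the comparison bullet say 5 weeks, so 65 days is the look-back that fits the rule as written.

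The lost pairs are also marginal. At most 6 days of their 29 to 35 day interval fall inside the window of interest. A rise that large should be uncommon, because the dose scheme in Protocol Section 12.3.2 already responds to a rise above 2 g/dL over 4 weeks. HemoCue values at Weeks 2 and 6 and unscheduled values give the other criteria further chances to classify the event. All of this stands and limits the size of the point.

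A reader might infer that 2.9% or 8.7% of events would be missed. The documents do not support that. These are counts of equally weighted day/interval combinations, which ignore the visit pattern, the distribution of Hgb and the other triggers. A reader might also take every pair with a later value on days -30 to -24 and an interval of 29 to 35 days to be lost. Of those 7 × 7 = 49 combinations, 28 are.

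Nor does it follow that thrombotic events drop out of the safety report. The same embolic and thrombotic term groups feed the separate special-interest category of death, myocardial infarction, stroke, heart failure and thromboembolic events, with no Hgb condition, although not every ischaemia term is on that list. Thromboembolic events are also adjudicated (Protocol Section 7.4.1).

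**Conclusion.** The inconsistency is real and minor. Section 10.6.4.3 sets a 5-week comparison and a 4-week retrieval window, which leaves retrieval 7 days short (65 against 58). Nothing elsewhere in the SAP corrects it. Only the 4 g/dL criterion is affected, and only for later values on days -30 to -24 paired with an earlier value before day -58.

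Few events are likely to change category. The documents give no frequency for such rises, so this is a judgement from the conditions that must coincide, not an estimate. The direction is certain, because widening the window can only add qualifying pairs.

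The output is a descriptive summary of adverse events of special interest. The primary non-inferiority test and the principal secondary test are untouched. The rule is the same in both arms, and nothing in the documents shows that the loss would favour one of them.

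**What to change.** In SAP Section 10.6.4.3, change the lower limit from 58 to 65 days before the event start in both places where it appears: the retrieval sentence and the condition on the earlier value. Change the explanatory 4 weeks to 5 weeks. The retrieval window then matches the stated comparison for every permitted pair. The cost is three small text edits and the matching date limit in the program, and no new data are needed. The change should be made before unblinding.

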5.2. Exclusion Criteria

A subject will not be eligible for participation in this study if any of the following criteria apply at screening or at randomization (Day 1), unless otherwise specified.

CKD-related criteria

1. **Kidney transplant:** Planned living-related or living-unrelated kidney transplant during the study.

Anemia related criteria

2. **Ferritin:** ≤ 100 ng/mL (≤ 100 $\mu\text{g/L}$) at screening or after IV iron supplementation.
3. **TSAT:** $\leq 20\%$ at screening or after IV iron supplementation.
4. **Vitamin B12:** Below the lower limit of the reference range at screening or after vitamin B12 supplementation.
5. **Folate:** < 2.0 ng/mL (< 4.5 nmol/L) at screening.
6. **Aplasia:** History of bone marrow aplasia or pure red cell aplasia (PRCA).
7. **Other causes of anemia:** Untreated pernicious anemia, thalassemia major, sickle cell disease, or myelodysplastic syndrome.
8. **Gastrointestinal (GI) bleeding:** Evidence of actively bleeding gastric, duodenal, or esophageal ulcer disease OR clinically significant GI bleeding ≤ 10 weeks prior to screening through to randomization (Day 1).

Erythropoiesis treatment criteria

9. Use of any ESA treatment within 8 weeks prior to screening except for limited use as part of dialysis initiation.

Limited use is defined as no more than 6 weeks of short acting ESA (rhEPO or biosimilars; maximum of 20000 U total) or long acting ESA (darbepoetin alfa [maximum of 100 μg total] or methoxy polyethylene glycol-epoetin beta [maximum of 125 μg total]) received before or after starting dialysis.

Cardiovascular disease-related criteria

10. **Myocardial infarction or acute coronary syndrome:** ≤ 10 weeks prior to screening through to randomization (Day 1).
11. **Stroke or transient ischemic attack:** ≤ 10 weeks prior to screening through to randomization (Day 1).
12. **Heart failure:** Chronic Class IV heart failure, as defined by the New York Heart Association (NYHA) functional classification system.
13. **Current uncontrolled hypertension:** Current uncontrolled hypertension as determined by the Investigator that would contraindicate the use of rhEPO.
14. **QTcB (Day 1):** QTcB > 500 msec, or QTcB > 530 msec in subjects with bundle branch block. There is no QTc exclusion for subjects with a predominantly ventricular paced rhythm.

Other disease-related criteria

15. **Liver disease (any one of the following):**
 - Alanine transaminase (ALT) $> 2x$ upper limit of normal (ULN) (screening only)

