7.4.4. Adverse Events of Special Interest

The investigator or site staff will be responsible for detecting, documenting and reporting any event that may represent the AEs of special interest listed below (using preferred terms):

- Thrombosis and/or tissue ischemia secondary to excessive erythropoiesis

- Death, myocardial infarction, stroke, heart failure, , thromboembolic events, thrombosis of vascular access
- Cardiomyopathy
- Pulmonary artery hypertension
- Cancer-related mortality and tumor progression and recurrence
- Esophageal and gastric erosions
- Proliferative retinopathy, macular edema, choroidal neovascularization
- Exacerbation of rheumatoid arthritis

The results of any investigation should be recorded on the AE page and in the relevant AE of special interest page of the subjects' eCRFs.

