
Potential Risk of Clinical Significance	Summary of Data/Rationale for Risk	Mitigation Strategy
	
Daprodustat is an inhibitor of CYP2C8: A clinical drug interaction study between 25mg and 100mg daprodustat with a CYP2C8 substrate (pioglitazone) showed that there is no PK interaction at these doses of daprodustat.
 
Daprodustat is a substrate of BCRP: Population PK analysis from Phase 2 studies suggested that while BCRP inhibitors were a covariate for daprodustat CL/F (8.6% lower clearance) the predicted change in exposure was not considered to be of clinical relevance.
 
Daprodustat is an inhibitor of OATP1B1/1B3: A clinical drug interaction study between 25mg and 100mg daprodustat with an OATP1B1/1B3 substrate (rosuvastatin) showed that there is no PK interaction at these doses of daprodustat
	
Other		
rhEPO risks (Control)	
 • See risks outlined in table for daprodustat for Excessive erythropoiesis (polycythemia) leading to thrombosis and/or tissue ischemia, Death, MI, stroke, thromboembolic events, thrombosis of vascular access, and for Increased cancer-related mortality and tumor progression. • Uncontrolled hypertension • Pure red cell aplasia 	
 • See mitigation strategies outlined in table for daprodustat for Excessive erythropoiesis (polycythemia) leading to thrombosis and/or tissue ischemia, Risk of death, MI, stroke, thromboembolic events, thrombosis of vascular access, and for Increased cancer-related mortality and tumor progression. • Specific eligibility criteria related to current uncontrolled hypertension are outlined in Section 5.2. • Specific eligibility criteria related to personal history of pure red cell aplasia are outlined in Section 5.2.

References:

Campochiaro PA. Ocular versus extraocular neovascularization: mirror images or vague resemblances. *Invest Ophthalmol Vis Sci.* 2006;47(2):462-74.

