10.6.4.3. Adverse Events

Adverse Events
AEs of Special Interest

Adverse events of special interest are classified as follows:
 
 Thrombosis and/or tissue ischemia secondary to excessive erythropoiesis Death, myocardial infarction, stroke, heart failure, thromboembolic events, thrombosis of vascular access Cardiomyopathy Pulmonary artery hypertension Cancer-related mortality and tumor progression and recurrence Esophageal and gastric erosions Proliferative retinopathy, macular edema, choroidal neovascularization Exacerbation of rheumatoid arthritis Worsening of hypertension

Adverse Events

Potential AESIs will be identified through a pre-defined terms of interest process in which pre-defined lists of AE preferred terms corresponding with each AESI will be used to identify events considered to be potential AESIs. Sites will be prompted via query to complete any necessary additional information for these AESIs in the eCRF.

For the category of thrombosis and/or tissue ischemia secondary to excessive erythropoiesis, after the terms of interest list has been applied, the additional Hgb criteria described below will be applied to identify only those events that are considered to be secondary to excessive erythropoiesis as meeting the AESI definition for thrombosis and/or tissue ischemia secondary to excessive erythropoiesis.

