
 ○ Haematological tumours of unspecified malignancy ○ Non-haematological tumours of unspecified malignancy ○ Malignant lymphomas 	
 ○ Uterine and fallopian tube malignant tumours ○ Uterine and fallopian tube tumours of unspecified malignancy

 ● Additional Preferred Terms: 
 ○ Aplastic anaemia ○ Cytopenia 	
 ○ Pancytopenia ○ Aplasia pure red cell
Esophageal and gastric erosions	

 ● High Level Terms: 
 ○ Duodenal ulcers and perforation ○ Gastric ulcers and perforation ○ Gastrointestinal ulcers and perforation, site unspecified ● Additional Preferred Terms: 
 ○ Haematemesis ○ Gastrointestinal haemorrhage ○ Upper gastrointestinal haemorrhage 	
 ○ Oesophageal ulcers and perforation ○ Peptic ulcers and perforation ○ Helicobacter duodenitis ○ Helicobacter gastritis ○ Melaena
Proliferative retinopathy, macular edema, choroidal neovascularization	

 ● Broad SMQ: Retinal disorders 	
Exacerbation of rheumatoid arthritis	

 ● High Level Term: Rheumatoid arthropathies ● Additional Preferred Terms: 
 ○ Rheumatoid factor increased ○ Rheumatoid factor positive 	

 ○ Rheumatoid factor quantitative increased 	
Worsening of hypertension	

 ● Narrow SMQ: Hypertension 	
Blood Pressure Events	

BP events will be identified during the study via programmatic sweeps of AE and SAE terms entered into the eCRF (using the narrow SMQ for hypertension). AEs identified this way will require an additional BP Exacerbation eCRF page to be completed that characterizes the event as clinically significant and/or symptomatic.
 
In addition, subjects that experience BP values that meet the following criteria at any visit will also be considered to have a BP event and be required to complete the Blood Pressure
	

CONFIDENTIAL

201410

Adverse Events

Exacerbation eCRF page:
 
 • SBP: an increase from baseline of ≥ 25 mmHg or SBP ≥ 180 mmHg • DBP: an increase from baseline of ≥ 15 mmHg or DBP ≥ 110 mmHg

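### The cancer AESI list counts four non-tumour haematological terms, one of them a named risk of the control drug, with no rationale and no step to remove non-cancer hits

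*SAP*

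**What the plan says.** Protocol 7.4.4 names the AESI "Cancer-related mortality and tumor progression and recurrence". SAP 10.6.4.3 turns it into a search list: a set of narrow tumour SMQs followed by additional preferred terms. The additional terms are "Aplastic anaemia", cytopenia, "Pancytopenia" and "Aplasia pure red cell".

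On how the lists work, the same SAP section says: "Potential AESIs will be identified through a pre-defined terms of interest process". Sites are then queried for any extra information needed. A further criterion, based on haemoglobin, is given for one category only; it is introduced by "For the category of thrombosis and/or tissue ischemia secondary to excessive erythropoiesis, after the terms of interest list has been applied".

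Protocol Appendix 4 (12.4), in the row for rhEPO (control) risks, lists "Pure red cell aplasia" as its own bullet, apart from the bullet that covers cancer. Protocol 5.2 also keeps the two apart: exclusion 6 covers a history of marrow aplasia or PRCA, and exclusion 16 covers malignancy.

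SAP 8.2.3.2 reports each AESI by arm as subjects with at least one event, number of events and rate per 100 person-years. A dot plot adds the relative risk of daprodustat against darbepoetin alfa with a 95% CI.

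**The concern.** A reader of the cancer AESI line will take it to count cancers. The SAP reads it the same way: for this category, 8.2.3.2 sets the competing risk as death that is not cancer-related. Four terms describing marrow failure or low cell counts do not fit that meaning, and the protocol itself treats one of them as a separate hazard of the comparator.

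Cancer is one of the named risks in Appendix 4. With about 150 subjects per arm followed for a year, few cancer events are likely, so one or two non-cancer hits could visibly move the estimate. What is at stake is how specific that comparison is, and whether its point estimate can be read as being about cancer.

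**Working it through.** The plan states no rate, count or power for this AESI, so there is no figure to reproduce. The check has two parts.

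**Tracing one event through the SAP.** Take a treatment-emergent PRCA event.

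1. Its preferred term is on the cancer list (SAP 10.6.4.3), so it is a hit.
2. The only stated filter after the list is the haemoglobin rule for thrombosis and tissue ischaemia. Nothing equivalent is stated for cancer, so the hit stays in.
3. It therefore enters the cancer count, rate and relative risk (SAP 8.2.3.2).
4. The cancer row of Protocol Appendix 4 deals with tumour growth, VEGF and carcinogenicity and does not mention marrow failure. No daprodustat row lists PRCA. The protocol thus gives no ground for treating PRCA as cancer.

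The same path applies to the other three terms, except that the documents link none of them to either drug.

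**Illustration of size.** From the protocol: 150 per arm (9.2.1). Everything else is assumed. With equal arms, RR = (a/150)/(b/150) = a/b, where a and b are subjects with an event on daprodustat and darbepoetin alfa. The 95% CI is exp(log RR ± 1.96 × SE), with SE = √(1/a − 1/150 + 1/b − 1/150).

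| True cancer subjects (daprodustat vs darbepoetin) | Added non-cancer subjects | RR (95% CI) |
|---|---|---|
| 3 vs 3 | none | 3/3 = 1.00 (0.21 to 4.88) |
| 3 vs 3 | 1 on darbepoetin | 3/4 = 0.75 (0.17 to 3.29) |
| 5 vs 5 | none | 5/5 = 1.00 (0.30 to 3.38) |
| 5 vs 5 | 1 on darbepoetin | 5/6 = 0.83 (0.26 to 2.67) |
| 5 vs 5 | 2 on darbepoetin | 5/7 = 0.71 (0.23 to 2.20) |
| 8 vs 8 | none | 8/8 = 1.00 (0.39 to 2.59) |
| 8 vs 8 | 1 on darbepoetin | 8/9 = 0.89 (0.35 to 2.24) |
| 6 vs 3 | none | 6/3 = 2.00 (0.51 to 7.85) |
| 6 vs 3 | 2 in each arm | 8/5 = 1.60 (0.54 to 4.78) |
| 6 vs 3 | 1 on daprodustat | 7/3 = 2.33 (0.61 to 8.85) |

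The shift can go either way, and every interval is wide.

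**Chance that PRCA occurs at all.** For an assumed risk p on darbepoetin alfa, the chance of at least one case in 150 is 1 − (1 − p)^150:

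- p = 0.01%: 1.5%
- p = 0.1%: 14%
- p = 0.5%: 53%
- p = 1%: 78%

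**The case against.** The best defence is that AESI lists are meant as sensitive screens. Other SAP categories are also broad: non-cardiac chest pain sits under myocardial infarction, and a positive rheumatoid factor under rheumatoid arthritis. Hits are called potential AESIs and sites are queried. Marrow terms might catch an undiagnosed blood cancer, and deleting them would cost sensitivity. This explains how the terms may have got there but does not settle the point. The list already holds SMQs for myelodysplastic syndrome, haematological tumours (malignant and unspecified) and malignant lymphomas. A screen needs a confirmation step before its hits are reported as the event, and none is stated for cancer. Moving the terms to their own line loses no event.

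Four stronger readings are tempting, and the documents do not support them.

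- *The list as a whole favours daprodustat.* Only PRCA is tied to a drug. The direction for the other three terms is unknown: equal occurrence dilutes a true difference, and an excess on daprodustat would count against it.
- *PRCA is a harm confined to the comparator arm.* Protocol 5.2 allows limited ESA use before entry in either arm, and 6.6.1 allows for non-study ESA during extended interruptions.
- *PRCA is hidden.* SAP 8.2.3.2 tabulates treatment-emergent events by arm and preferred term, so a case appears by name. It lacks only a line of its own in the AESI display, and Protocol 7.4.4 does not make PRCA an AESI.
- *The cumulative incidence plots are distorted.* They are optional and are not made with fewer than 20 subjects across both arms. The largest total in the table above is 8 + 9 = 17.

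It also stands that every interval in the illustration is far wider than the shift from one or two events.

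**Conclusion.** The point holds as a matter of classification. Four terms that are not tumour terms count toward the cancer AESI, without a rationale or a confirmation step, and the protocol names one of them as a control-drug risk distinct from cancer. The cancer count, rate and relative risk are less specific as a result. A shift toward daprodustat follows for PRCA only, and only if it occurs on darbepoetin alfa.

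The size cannot be derived from the documents and may be zero, since subjects with a history of marrow aplasia or PRCA are excluded and the comparator arm has about 150 subjects. The ratios shown rest wholly on assumed counts. A subject who has both a cancer and one of the four terms is counted once in the subject-level figures, so only subjects without a tumour-term hit add to them.

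Protocol 9.4.2.2 makes the safety analysis descriptive. Neither the haemoglobin non-inferiority test nor the IV iron test is touched. This is a minor point, worth acting on because it is cheap to settle.

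**What to change.** Before unblinding, do one of the following in SAP 10.6.4.3 and 8.2.3.2:

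- take the four terms out of the cancer AESI count and show them as a separate haematological line (marrow failure/PRCA) in the AESI table; or
- keep the list as it is, state why the terms are on it, and add a cancer AESI summary and relative risk without them.

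Either is an edit to a term list or one added display, with no new data. The cost is one extra line or table. The first option also departs slightly from the existing term list and shows a line that is not among the AESIs in Protocol 7.4.4, which a footnote can explain.
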